Knee Strengthening With Hip vs. Ankle Exercises in Women With Patellofemoral Pain Syndrome

September 25, 2025

1 **Abstract**

2 **Purpose:** This study compared the effects of knee strengthening combined with either hip or ankle
3 joint exercises on dynamic knee valgus (DKV), visual analogue scale (VAS) scores during activity,
4 tendon stiffness, muscle structure, ankle range of motion, and muscle strength in women with anterior
5 knee pain. **Methods:** Forty-five female recreational athletes aged 20–40 with anterior knee pain were
6 randomly assigned to three groups: hip + knee exercises (HK group, n = 15), ankle + knee exercises
7 (AK group, n = 15), and stretching alone (control group, n = 15). The HK and AK groups received
8 supervised telehealth-based exercise sessions (30 minutes/day, 3 times/week for 8 weeks), while the
9 control group received only an educational pamphlet. Assessments were conducted at baseline, 4
10 weeks, and 8 weeks.

11

12 **Key Words:** (1) Dynamic alignment (2) Tele-rehabilitation (3) Pain modulation (4) Muscle strength.

13 **Introduction**

14 Anterior knee pain refers to clinical symptoms of pain around the patella that occur during
15 activities such as squatting, running, and climbing stairs due to increased pressure on the
16 patellofemoral joint. Anterior knee pain is a non-contact knee injury, typically characterized by a
17 gradual onset of pain around the knee joint that is not related to trauma. Additionally, the pain tends to
18 worsen with increased activity, leading to limitations in movement and reduced exercise performance
19 (1, 2). Statistics show that this condition accounts for 25-40% of all knee injuries, with a significantly
20 higher prevalence in women than in men (3). This may be related to anatomical differences,
21 particularly the larger knee valgus angle in women. Additionally, characteristics such as muscle
22 strength and muscle coordination in women may also contribute to greater knee joint instability,
23 further increasing the risk of anterior knee pain, impacting quality of life, and raising healthcare costs
24 (4-6).

25 Treating anterior knee pain is particularly challenging because multiple factors cause it. There is
26 currently no consensus on treatment strategies, but scholars generally agree that the primary causes of
27 anterior knee pain include increased dynamic knee valgus (DKV) angle, weakness in the knee and hip
28 muscles, and poor landing mechanics (7-9). Although the pain associated with anterior knee pain
29 primarily occurs in the anterior knee, the underlying causes are not limited to the knee joint but also
30 involve the hip and ankle joints. Therefore, treatment strategies need to be multifaceted, such as
31 combining hip and quadriceps strengthening, foot and ankle mobility exercises, movement retraining,

32 and patient education, which together target both proximal and distal factors contributing to
33 patellofemoral pain (10-14).

34 Recent studies have shown that hip muscle control and ankle dorsiflexion range of motion
35 (ROM) influence the DKV angle during weight-bearing activities (15). In the top-down kinetic chain
36 theory, the hip abductor and external rotator muscles eccentrically contract to control hip adduction
37 and internal rotation (16). When these muscles are weak, poor neuromuscular control during
38 weight-bearing activities can lead to increased femoral adduction and internal rotation, increasing the
39 lateral force on the patellofemoral joint (17, 18). This results in excessive load on the patellar tendon
40 and facet joints, which is a key factor in anterior knee pain development (19-21). Numerous studies
41 have demonstrated that weakness in the hip abductor and external rotator muscles can lead to patellar
42 rotation and instability (19, 20). In research by Ferber and colleagues, a three-week hip abduction
43 muscle training program for anterior knee pain patients alleviated knee pain and increased knee
44 stability more quickly than the group that only received knee joint training (22). Furthermore,
45 randomized controlled trials have shown that quadriceps training combined with hip abduction and
46 external rotation muscle training is more effective in reducing knee pain than quadriceps training
47 alone (23, 24). The existing evidence suggests that training both the hip and knee joint muscles is
48 more effective than training the hip muscles alone. Additionally, hip muscle training alone is slightly
49 more effective than knee joint training alone (25). Therefore, studies recommend incorporating hip
50 muscle training into the training programs for anterior knee pain patients (21, 26, 27).

51 On the other hand, in the bottom-up kinetic chain theory (2), ankle dorsiflexion ROM and the
52 strength of the ankle plantar flexor muscles play crucial roles in absorbing ground reaction forces
53 during landing (28, 29). When ankle dorsiflexion is restricted, patients may compensate for the
54 sagittal plane movement deficiencies by increasing the coronal plane movement (30). In other words,
55 when ankle joint angles are limited, the knee joint may increase the DKV angle as a compensatory
56 strategy, leading to a stiffer landing strategy that increases the knee joint's exposure to greater ground
57 reaction forces during weight-bearing, thereby increasing the risk of anterior knee pain (31, 32). In a
58 proper landing process, the forefoot hits the ground, followed by the eccentric contraction of the
59 plantar flexor muscles to assist in ankle dorsiflexion. Thus, the eccentric contraction capacity of the
60 posterior lower leg muscles also plays a crucial role during weight-bearing (33). In other words,
61 restricted ankle dorsiflexion can affect the entire lower limb kinetic chain, increasing the risk of
62 anterior knee pain.

63 In daily life or sports environments, single-leg landing is a common movement in many jumping
64 activities. During landing, if the ankle dorsiflexion angle is restricted, the forward glide of the tibia is
65 reduced, requiring compensatory hip adduction and internal rotation (34). This movement pattern in a
66 closed kinetic chain leads to dynamic knee valgus, increases friction along the patellar tracking path,
67 reduces the lower limb's shock absorption capacity, and subjects the patellar tendon to greater ground
68 reaction forces, leading to anterior knee pain (35). Therefore, the single-leg landing test (SLL) is
69 often used to assess lower limb dynamic alignment and evaluate the DKV angle. Compared to

70 single-leg squat tests or step-down tests, the SLL better reflects the actual lower limb alignment
71 during athletic movements (36).

72 A literature review reveals that only one study has shown that a single session of ankle joint
73 exercise intervention and relaxation can effectively increase ankle dorsiflexion ROM and reduce
74 DKV (37). However, the cases in that study did not involve anterior knee pain, and the intervention
75 was limited to single-session immediate effect. Currently, there is a lack of high-level evidence in the
76 literature to demonstrate that improving the muscle strength around the hip joint and the mobility of
77 the ankle joint can reduce DKV and thereby alleviate the clinical symptoms of anterior knee pain.

78 Notably, there is only one study that specifically explores the relationship between ankle joint
79 interventions, DKV, and anterior knee pain, and this study only examines the effects immediately
80 postintervention (31). More importantly, as mentioned earlier, most assessments focus on changes in
81 pain and biomechanics. To date, no studies have investigated the long-term effects of exercise
82 interventions on the structural changes in the hip, knee, and ankle soft tissues or explored the potential
83 mechanisms of recovery.

84 Telemedicine is a simple rehabilitation method that overcomes spatial limitations. Particularly
85 during the COVID-19 pandemic, to reduce the risk of face-to-face transmission, many patients were
86 unable to continue their rehabilitation at hospitals (38). As a result, telemedicine became an
87 alternative solution, allowing patients to continue their rehabilitation. Telemedicine not only
88 effectively reduces treatment costs but also improves patient adherence to treatment (39, 40).
89 Telehealth-delivered physical therapy, including telerehabilitation, has been shown in randomized

90 trials to be as effective as face-to-face care for musculoskeletal conditions—yielding comparable
91 improvements in pain, physical function, and quality of life—while systematic reviews report similar
92 outcomes across a broad range of conditions such as low back pain and knee osteoarthritis (41). These
93 findings demonstrate that physical therapy programs can be effectively and successfully administered
94 via telehealth in musculoskeletal populations (42, 43). Although some literature indicates that
95 telemedicine is effective in alleviating pain and improving knee function in anterior knee pain
96 patients, there is still a lack of high-level evidence to support this, and most studies have focused
97 solely on clinical symptoms (44). Therefore, this study adopted 8 weeks of telemedicine as an
98 intervention strategy to further understand the benefits of combining hip or ankle joint exercises on
99 exercise performance, clinical symptoms, and tissue structure in female patients with anterior knee
100 pain. We hypothesized that 8 weeks of telehealth-based supervised exercise, both the hip and ankle,
101 coupled with knee strengthening, would effectively improve DKV and pain in women with anterior
102 knee pain, and both groups would provide comparable benefits.

103

104 **Methods**

105 All participants provided written informed consent for this study, which was approved by the
106 Institutional Review Board of Kaohsiung Medical University Chung-Ho Memorial Hospital
107 (Approval Number: KMUIRB-E(I)-20220334). Before the formal trial begins, the examiners
108 received comprehensive testing training. Each participant will also be familiarized with all
109 experimental procedures and testing items.

111 Participants

112 A total of 45 female recreational athletes with anterior knee pain were recruited. We only
113 included females in the current study due to their approximately twice the risk of anterior knee pain
114 compared to males (3). Cases were required to be evaluated by orthopedic or sports medicine
115 physicians to confirm the diagnosis of anterior knee pain. To exclude the possibility of joint
116 degeneration, the participants' age was restricted to 20-40 years. Recreational athletes were defined as
117 individuals who participate in aerobic exercise or physical activities at least three times per week for
118 a minimum of 30 minutes per session. Inclusion Criteria: (1) Female recreational athletes aged 20-40
119 years who engage in regular exercise; (2) Experiencing pain in the anterior or surrounding patella
120 during at least two or more of the following activities: walking, running, jumping, kneeling, squatting,
121 climbing stairs, or prolonged sitting; (3) A pain index of 3 or higher on the Numeric Pain Rating Scale
122 (NPRS) and symptoms persisting for at least 3 months; (4) Knee pain unrelated to trauma. Exclusion
123 Criteria: (1) Inability to operate a smartphone or computer; (2) History of fractures or surgeries
124 involving the hip, knee, ankle, or foot; (3) History of meniscus, knee ligament injuries, or ankle
125 sprains within the last six months; (4) Knee ligament laxity, inflammation, swelling, patellar
126 dislocation, or subluxation; (5) Cognitive impairment or inability to follow simple instructions; (6)
127 History of cardiovascular or neurological disorders; (7) Advised by a physician to avoid exercise. Use
128 of over-the-counter pain medication was not an exclusion criterion. Participants were instructed to
129 maintain their usual medication habits and to refrain from initiating new oral analgesics for knee pain

130 during the intervention period. At baseline, no participants reported regular use of oral analgesics for
131 anterior knee pain, and no changes in medication use were reported during the study.

132

133 Experimental Procedure and Random Grouping

134 A single-blinded randomized controlled trial was conducted, in which outcome assessors were
135 blinded to group allocation to reduce the risk of bias. Upon arrival at the research laboratory,
136 participants first performed a simple warm-up (5 minutes of cycling) before immediately undergoing
137 pre-tests. The measurements were conducted in the following order: pain index assessment, patellar
138 tendon stiffness measurement, ultrasound examination, ankle joint ROM measurement, DKV angle
139 measurement, and maximum muscle strength measurement. After completing the pre-test (T0),
140 participants randomly drew a numbered card from an opaque box to determine their group
141 assignment for the subsequent 8-week exercise intervention: Group A (ankle + knee joint exercise
142 group, AK), Group B (hip + knee joint exercise group, HK), or Group C (stretching group). After
143 grouping, participants were immediately instructed on and performed the assigned exercise
144 intervention once. Following three training sessions per week, post-tests (same as pre-tests) were
145 conducted at the 4th week (T1) and the 8th week (T2) (Figure 1). Throughout the exercise training
146 period, participants were guided and monitored by a professionally trained physical therapist.

147

148 Interventions

149 Participants in the hip + knee joint exercise group (HK group) and the ankle + knee joint exercise
150 group (AK group) received one-on-one exercise instruction from a physical therapist with a
151 background in sports medicine. The exercise training goals for the HK group included strengthening
152 the knee extensors (Figure 2(a) Primarily targets the quadriceps (knee extensors), improving knee
153 extension strength and stability 2(b) Also strengthens the quadriceps, with greater isolation of the
154 knee extensors compared to (a), focusing on controlled terminal knee extension 2(c) Works
155 the quadriceps, gluteal muscles, and to some extent the hamstrings, emphasizing closed-chain
156 strengthening and functional loading of the lower limb, while also training postural control), hip
157 external rotators (Figure 3(a) Strengthens the hip abductors (particularly gluteus medius) while
158 promoting pelvic stability during lateral movement 3(b) Activates the gluteus maximus and posterior
159 chain muscles, with added hip abductor engagement from the resistance band 3(c) Specifically targets
160 the hip external rotators (gluteus medius, gluteus minimus, piriformis) to improve control of hip
161 rotation and reduce dynamic knee valgus 3(d) A progression of (a) that increases challenge to the hip
162 abductors and lateral stabilizers, requiring greater control at the knee and ankle 3(e) Glute bridge with
163 one leg raised using a resistance band – An advanced form of (b), training unilateral gluteal and core
164 strength, while also engaging hip abductors and extensors for pelvic stabilization 3(f) Isolates
165 the gluteus medius and hip abductors, critical for controlling frontal-plane motion and stabilizing the
166 pelvis during single-leg tasks), and hip abductors (Figure 3). For the AK group, the training goals
167 included strengthening the knee extensors (Figure 2), ankle dorsiflexors (Figure 4(a) Strengthens
168 the ankle plantarflexors (gastrocnemius, soleus), improving calf strength and lower-limb push-off

169 power 4(b) A progression of (a) that further develops plantarflexor strength and enhances ankle
170 stability and balance under unilateral loading 4(c) Increases ankle dorsiflexion ROM by mobilizing
171 the talocrural joint, improving tibial forward glide during weight-bearing 4(d) Strengthens
172 the dorsiflexor muscles (tibialis anterior, extensor digitorum longus), enhancing control of foot
173 clearance during gait and landing 4(e) Stretches the gastrocnemius–soleus complex, improving ankle
174 flexibility and reducing compensatory movement patterns), and plantar flexors (Figure 4), as well as
175 performing ankle joint self-mobilization and stretching exercises (Figure 4). The therapist ensured
176 that the participants were familiar with and correctly performing the exercises before they left. At the
177 end of the session, participants were provided with a home exercise demonstration handout to be
178 performed three times per week for eight weeks. The handout included precautions to take during
179 exercise, guidelines for managing exercise injuries, and a contact number for consultation.

180 Home exercise training was remotely supervised. During the home exercise period, participants
181 engaged in moderate-intensity exercise (rate of perceived exertion, RPE, 12-14) three times per week.
182 Each exercise was performed in two sets, with each set consisting of 10-15 repetitions according to
183 the training plan, and the total exercise time was approximately 30-45 minutes. The therapist used
184 communication software to supervise participants one-on-one remotely, guided them through the
185 exercises, monitored their RPE, and provided individualized, gradual adjustments as needed. The
186 therapist also corrected participants' posture and movements if necessary and adjusted the length or
187 resistance of the resistance bands to increase or decrease exercise intensity based on the participants'
188 abilities.

189 Participants in the stretching group received a knee exercise handout and were instructed on
190 quadriceps and hamstring stretching exercises at baseline. Unlike the HK and AK groups, no remote
191 supervision, monitoring, or follow-up was conducted for the stretching group. This group functioned
192 as the unsupervised control condition.

193

194 Outcome measures

195 *Primary Outcome (DKV)*

196 The Single Leg Landing Task (SLL) was used to measure the DKV angle during single-leg landing.
197 The participant stood on a 30 cm box and first bent the non-testing leg's knee to approximately 90
198 degrees. After stabilizing, the participant jumped forward with the testing leg to a target 10 cm away
199 from the box, maintaining balance for five seconds upon landing. During the test, the non-testing leg
200 was not allowed to touch the ground, the participant was instructed to keep their eyes looking forward,
201 and both arms were crossed over the chest to minimize the influence of arm movement. The entire
202 sequence was repeated twice, and video recordings were made using a smartphone (45). Image
203 Analysis: Before recording, markers were placed on the midpoint of the knee joint (midpoint of the
204 line connecting the medial and lateral femoral condyles), the midpoint of the ankle joint (midpoint of
205 the line connecting the medial and lateral malleoli), both anterior superior iliac spines (ASIS), and the
206 midpoint of the line connecting the ASIS and the knee joint. A smartphone camera was positioned 2
207 meters in front of the participant to record the video. The video was then analyzed using Kinovea
208 software version 0.8.27 (<https://www.kinovea.org/download.html>) to measure the two-dimensional

209 frontal plane projection angle (FPPA). The knee valgus angle was calculated by subtracting the
210 obtained angle from 180 (the larger the value, the greater the knee valgus angle). The sequence was
211 repeated twice, and the average value was taken.

212 *Secondary outcomes*

213 Numeric Pain Rating Scale (NPRS): The NPRS is an 11-point scale where 0 indicates no pain
214 and 10 indicates the worst pain imaginable. Participants were asked to rate their perceived pain both
215 at rest and during weight-bearing in a lunge position (46, 47).

216 Patellar Tendon Stiffness Measurement: The stiffness of the patellar tendon was assessed using a
217 handheld device (MyotonPRO; Tallinn, Estonia). Participants were seated at the edge of a bed with
218 their knees bent at 90°. The tension was measured 3 cm below the apex of the patella, with the
219 assessment repeated three times. The average value was taken as the patellar tendon stiffness (48).

220 Muscle structure: A portable ultrasound device (Linear wireless probe LU700L VET) was used
221 to assess the structure of the gastrocnemius and gluteus medius muscles in a resting state. Ultrasound
222 images were used to record muscle thickness (MT) and pennation angle (PA). The pennation angle
223 was defined as the angle between the deep fascia and muscle fibers. Muscle thickness was defined as
224 the length of a perpendicular line drawn from the origin of the muscle fibers at the deep fascia to the
225 superficial fascia, based on the pennation angle (49). Gastrocnemius: Participants lay prone on a bed
226 with a towel placed under the knee to flex it to 20°-30°, and the ankle was fixed at 90° using a
227 goniometer. The ultrasound probe was placed parallel to the gastrocnemius muscle fibers, and the
228 scanning depth was adjusted to 6.3 mm to display both the deep and superficial fascia. The pennation

229 angle was defined as the angle between the deep fascia and muscle fibers. Muscle thickness was
230 measured as the length of a perpendicular line drawn from the origin of the muscle fibers at the deep
231 fascia to the superficial fascia (49). Gluteus Medius: Participants lay on their side, with the test leg on
232 top, and the hip and knee joints in a neutral position. The ultrasound probe was placed between the
233 iliac crest and the greater trochanter, parallel to the gluteus medius muscle fibers. The greater
234 trochanter was positioned in the lower right third of the image as a landmark to increase measurement
235 consistency, with the gluteus medius centered in the image for recording (50).

236 Ankle Joint ROM: Since patients with anterior knee pain often experience knee pain during
237 weight-bearing activities, this study used a weight-bearing lunge test to measure the active
238 dorsiflexion angle of the ankle during weight-bearing. A measuring tape was placed on the floor, with
239 the participant's heel and second toe aligned with the tape. The participant started with their toes 10
240 cm from the wall, touching the wall with the knee while keeping the heel on the ground. The heel
241 must maintain contact with the floor. If the participant could easily touch the wall or could not reach it,
242 the distance was adjusted by 1 cm increments, gradually adjusting the distance forward or backward
243 according to the participant's ability until they could no longer keep the heel fully in contact with the
244 ground. At the maximum angle, a goniometer was used for measurement, with the fixed arm placed
245 flat on the ground and the movable arm aligned with the line connecting the lateral malleolus and the
246 head of the fibula. The test was repeated twice, and the average value was recorded (51).

247 Maximum Voluntary Isometric Strength: A handheld dynamometer (MicroFET3; Hoggan
248 Scientific LLC, USA) was used to measure the maximum isometric strength of the hip abductors,

249 knee extensors, ankle dorsiflexors, and ankle plantar flexors. Each test was repeated twice, and the
250 average value was recorded (52).

251

252 Statistics

253 The sample size for this experiment was estimated using G*Power and calculated using the priori
254 sample size for Repeated Measures ANOVA. The effect size (ES) was set at $f = 0.45$, with an alpha
255 value of 0.05 and a power of 80%. Based on the above calculations, the required sample size was 36
256 participants. Considering a potential 10% dropout rate, 40 eligible participants were to be recruited.
257 However, to increase the statistical power, the final target was to recruit 45 participants.

258 Data processing and analysis were conducted using SPSS 20.0 for Windows statistical software.
259 The significance level for all data was set at $p < 0.05$, and all numerical data were presented as mean
260 \pm standard deviation. The Shapiro–Wilk test was used to determine the normality of the data
261 distribution. If the data were normally distributed, a two-way ANOVA with repeated measures was
262 used to analyze the 3 group factors (hip + knee group, hip + ankle group, stretching group) \times 3 time
263 factors (pre-test, week 4, post-test) to first examine the significance of the interaction effect. If the
264 interaction effect was significant, indicating that the group and testing time factors influenced each
265 other, a simple main effect test and Bonferroni post hoc comparisons were performed. A One-way
266 ANOVA analysis was used to compare intra-group differences before the intervention, followed by
267 Bonferroni post hoc comparisons. Training adherence was calculated using the formula: (actual

268 training sessions/24) * 100%. Test-retest reliability was verified using the Intraclass Correlation
269 Coefficient (ICC) to ensure the consistency of all measurements.

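### The hypothesis expects hip + knee (HK) and ankle + knee (AK) to give comparable benefits, but the plan has only tests of difference, which can contradict that clause and cannot support it

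*Combined protocol and SAP*

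**What the plan says.** The title sets the two active programmes against each other: "Knee Strengthening With Hip vs. Ankle Exercises in Women With Patellofemoral Pain Syndrome". The last paragraph of the Introduction predicts that both will improve DKV (the primary outcome) and pain, "knee pain, and both groups would provide comparable benefits". Comparable is not defined there or elsewhere.

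The Statistics section plans a 3 group × 3 time repeated measures ANOVA, "to first examine the significance of the interaction effect". If the interaction is significant, "a simple main effect test and Bonferroni post hoc comparisons were performed". Nothing is stated for a non-significant interaction. The only other group test is a one-way ANOVA on the pre-intervention data. "The significance level for all data was set at" p < 0.05, and numerical data are to be shown as mean ± SD.

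The sample size rests on a repeated measures ANOVA with f = 0.45, which is not tied to HK versus AK or to a number of degrees of DKV. Pain is scored on the NPRS in two conditions, "at rest and during weight-bearing in a lunge position", and the hypothesis does not say which is meant.

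**The concern.** A test of difference starts from the null of no difference. A significant result counts against comparability. A non-significant result leaves the question open unless the estimate is precise enough to exclude differences that matter, and the plan names neither the estimate nor the differences that matter. The clause can therefore be refuted under the plan but not confirmed.

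At stake is the comparison in the title. If the HK versus AK comparison comes out at p > 0.05, or is never run because the interaction was not significant, nothing in the plan stops the report from saying that the hypothesis of comparable benefit was borne out. A clinician could then treat the two programmes as interchangeable on data that are compatible with a sizeable difference.

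**Working it through.** **Inputs from the documents.** 15 per arm (Abstract: "AK group, n = 15), and stretching alone (control group, n = 15", and the same for HK); three arms, hence three pairs for Bonferroni; alpha 0.05; f = 0.45, power 80%, required N 36, 40 after 10% dropout, final target 45 (Statistics).

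**Assumptions, because the documents give no figures.** Differences are in units of the outcome's between-person SD. No dropout. HK versus AK is compared at week 8 without baseline adjustment, because the plan states none.

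**1. The plan's own figure.** N = 36 can be reproduced. With the between-groups option, three measurements and an assumed correlation of 0.5, λ = f² × N × 3 / (1 + 2 × 0.5) = 0.2025 × 36 × 3 / 2 = 10.94 on 2 and 33 df, giving power 81.4%. With an SPSS-type interaction effect size, λ = f² × (N − 3) × 2 = 0.2025 × 33 × 2 = 13.37 on 4 and 66 df, giving 81.8%. Dropout: 36 / 0.9 = 40. The arithmetic is sound, but neither reading sizes the trial for HK versus AK.

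**2. Precision of HK minus AK.** SE = √(2/15) = 0.365 SD. The 95% half-width is t(0.975, 28 df) × SE = 2.048 × 0.365 = 0.75 SD (0.74 with the three-arm error term on 42 df). An observed difference of zero would be compatible with a true difference of up to about 0.75 SD either way.

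**3. How often a real difference is missed.** Bonferroni for three pairs uses alpha 0.05/3, so the critical t on 42 df is 2.494. The non-centrality is d / 0.365.

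| True HK–AK difference | Non-centrality | Chance of a non-significant result |
|---|---|---|
| 0.5 SD | 1.37 | 86% |
| 0.95 SD | 2.60 | 45% |
| 1.0 SD | 2.74 | 40% |

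**4. What the tests can show.** Significance requires an observed gap of at least 2.494 × 0.365 = 0.91 SD. A gap that large would count against comparability on most readings. Below it, the planned test gives no verdict.

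**5. What a comparability criterion could deliver at 15 per arm.** Suppose the arms are truly identical and comparable is concluded only if the interval lies wholly inside the margin. By numerical integration over the sample variance (28 df):

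| Assumed margin | 90% CI inside | 95% CI inside |
|---|---|---|
| ±0.5 SD | 0.6% | 0.03% |
| ±0.8 SD | 38% | 16% |
| ±1.0 SD | 70% | 51% |

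An 80% chance at ±0.5 SD needs 70 per arm with a 90% interval or 86 with a 95% interval.

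**6. Effect of baseline adjustment.** If baseline and week-8 values correlate at r, the half-width shrinks by √(1 − r²): 0.748 × √0.75 = 0.65 SD at r = 0.5, and 0.748 × √0.51 = 0.53 SD at r = 0.7. This helps but does not change the conclusion.

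**The case against.** The strongest reply is that comparable is an informal word in one clause of the Introduction. The Abstract's purpose is only to compare effects, and improvement is tested properly. That limits the weight of the point but does not remove it: the clause belongs to the stated hypothesis, covers the primary outcome and concerns the comparison in the title. If it was meant informally, restating it as estimation costs nothing.

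Three stronger readings are tempting, and the documents do not support them.

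- *The sponsor plans to read p > 0.05 as comparability.* No passage says so. The gap is that the plan does not rule it out.
- *A reader would have no means of judging the clause.* Arm means, SDs and numbers would let a reader derive an unadjusted HK minus AK interval at each visit. What is missing is a prespecified contrast and a criterion for judging it.
- *The interaction step will often block the HK versus AK comparison at the effect the trial was sized for.* The plan does not say which effect f = 0.45 describes, so no such rate follows from it. If f is the SPSS-type interaction effect that reproduces N = 36, power for the interaction at N = 45 is about 91%. If f describes time-averaged group differences, the implied week-8 effects are larger and the interaction would seldom be missed. The defensible point is that the plan is silent on what happens when the interaction is not significant.

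**Conclusion.** The point holds for the comparability half of the hypothesis only. As written, the plan can contradict that clause and cannot support it. This follows from the text and would be true at any sample size, since no margin or interval is specified.

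The numbers show why non-significance must not fill the gap. At 15 per arm the week-8 interval is about ±0.75 SD, and a true 0.5 SD difference goes undetected about 86% of the time. Differences near 1 SD are missed less often, about 45% at 0.95 SD, so the trial is not blind to very large differences. These figures assume SD units, complete data and an unadjusted comparison; the margins in the working are illustrative. The sample size arithmetic and the analysis of improvement are not in question. This should be fixed because it is cheap and changes what the trial may conclude about its title comparison.

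**What to change.** 1. For DKV (in degrees) and NPRS (stating rest, lunge or both), report the HK minus AK difference at week 8 with its 95% confidence interval, whatever the interaction result. Baseline adjustment is optional and would narrow the interval.
2. State that p > 0.05, or a comparison not performed, will not be reported as comparable benefit.
3. State whether outcome data have been examined, since the Participants section describes recruitment and the course of the study in the past tense.
   - *If not examined:* restate HK versus AK as an estimation objective. Alternatively, fix a justified margin for each outcome and the interval level in advance, and conclude comparable only if the interval lies wholly inside the margin.
   - *If examined:* keep the original hypothesis on record, label any change as post hoc, and report estimates and intervals without a comparability conclusion.

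**Cost.** Some wording and one added estimate and interval per outcome, with no extra participants or visits. The downside is a less favourable headline for HK versus AK, and little chance of concluding comparability under a tight margin at 15 per arm.
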